develop and test a prototype version of *OnTrack>An Online Role-Playing Game* (*OnTrack>The Game* or *OTG*), an online role-playing game designed for youth and young adults experiencing FEP. The Phase I SBIR (NIMH #1R43 MH105013-01) brought together C4's experience developing innovative learning technologies with the subject matter expertise of [name] and her team. Phase I showed positive changes in quantitative measures of hope and recovery, as well as an enthusiastic response to the prototype as evidenced by qualitative interviews (see *Significance* section in full proposal). These findings suggest the need for and feasibility of conducting a Phase II study.

The proposed mixed-methods Phase II study will use standardized measures and semi-structured qualitative interviews to achieve the following aims:

1. **Product aim:** To refine, expand, and finalize *OnTrack>The Game*. Building on the Phase I prototype, we will improve functionality, expand the play spaces and levels, add interaction with non-player characters, include more resources on FEP, and expand the library of videos on hope and recovery.
2. **Primary research aim:** To evaluate the effectiveness of a role-playing game (*OTG*) in increasing empowerment, decreasing stigma concerns, and improving treatment engagement.

Hypothesis 1: Compared to control condition (Recovery Videos, or *RV*), participants in *OTG* will report significantly increased empowerment at 2 months post-intervention compared to baseline.

Hypothesis 2: Compared to the control condition (*RV*), participants randomized to the *OTG* condition will report significantly increased empowerment, (Herth Hope Index, Recovery Attitude Questionnaire, Roger's Empowerment Scale), decreased stigma concerns (Questionnaire on Anticipated Stigma, Rüschi Stigma Stress), and greater treatment engagement (Signh O'Brien Level of Engagement Scale, engagement with CSC program) at the 5-month follow-up compared to baseline.

3. **Secondary research aim:** To determine if changes in empowerment and stigma concerns mediate the effect of *OnTrack>The Game* on treatment engagement.

Hypothesis 3: Increases in hope, attitudes toward treatment, and self-efficacy and decreases in stigma concerns at post-treatment will partially mediate the improvement in treatment engagement at follow-up.

METHODS

Research Design

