Client interviews: A subset of 10 clients from each study condition (n=20) will be asked to participate in semi-structured interviews after using *OTG* or *RV*. Questions will explore their experiences in using the product (navigation and access, preferences, facilitators and barriers to use); attitudes toward treatment and working with their clinician; and their feelings of self-efficacy, recovery, hope for the future, and stigma. Clients will receive \$25 for participating in these interviews.

Clinician interviews: Ten clinicians, working with clients from both study conditions, will also be asked to participate in semi-structured interviews to explore their experiences in working with clients from each condition and changes in attitudes they may have observed, barriers and facilitators to use of each product, and feedback on the product components. Clinicians will receive \$50 for participating in these interviews.

We feel that the number of interviews described will be sufficient to reach data saturation, but we will add interviews if needed.

Quantitative: Baseline, post, and follow-up surveys will be completed with each study participant via in-person interviews using direct data entry into a secure online database built with Qualtrics software. Baseline assessment will occur at the time informed consent is obtained if possible, and at this time we will ask participants for demographic data including age, gender, race and ethnicity, education level, relationship/marital status, work, and school participation. Data on treatment engagement will be extracted from clinic charts.

The following table presents domains, measures, and time-points for administering them.

Quantitative Measures and Frequency of Assessments by Specific Aim				
Domain	Measure	Administered at study time-point		
		BL	Post	Follow-up
Aims 2 and 3				
Stigma Concerns	Rüsch Stigma Stress	x	x	x
	Questionnaire on Anticipated Discrimination			
Empowerment	Recovery Attitude Questionnaire (RAQ)	x	x	x
	Roger's Empowerment Scale Total			
	Herth Hope Index (HHI)			
Treatment Engagement	Singh O'Brien Level of Engagement Scale (SOLES)	x	x	x

	Number of unduplicated visits during the follow-up period is above engagement threshold			x
Description of Sample and Potential Moderators and Mediators				
Participant Demographics	Demographic Form/Chart Review	x		
Experience with Game Functionality and Design	EGameFlow		x	x
Use of Game/Website	Springroll Learning Module/Google Analytics		x	x

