Data Analysis

All data will first be screened for errors via frequency and contingency tables and univariate and bivariate plots. These will also allow us to check for missing data and that variable distributions are compatible with the statistical models we will use.

Triangulation increases confidence in the validity of a finding if it converges across disparate sources of information. Qualitative data will be triangulated by sources (comparing client and clinician interview data). Further, the research team will also actively work to integrate quantitative and qualitative datasets, comparing results during and after analysis, to allow for ongoing interpretation.

We will use a mixed-effects, 2-level model (SAS Proc Mixed, GLIMIX) to test primary hypotheses with a random class effect to account for intra-team correlation (ICC). The longitudinal assessments (baseline (t=1), post-treatment (t=2), and 6-month follow-up (t=3)) will be nested within participants and participants nested within teams. Adjustment for baseline response will reduce residual variation at t=2 and t=3 resulting in greater power. Correlation in the response at t=2 and t=3 (conditional on response at t=1) will be modeled by allowing the corresponding error terms to be correlated rather than using a random individual effect. That is, we will use a hybrid model with both a random class effect and correlated error terms (conditional on baseline value and the class effect).

Quantitative Analysis

Aim 2: A Generalized Linear Mixed Model will be used with the outcome measures listed above as the dependent variables and treatment group (*OTG* vs. *RV*) as the independent variable of interest. Baseline outcome measures and any covariates determined from preliminary analyses will also be included in the model. Post hoc analyses will include assessment of treatment group differences in the outcome measures at post-intervention and 3-month follow-up. Engagement will be binary variable; therefore a log link will be employed. The test of hypothesis 1 and 2 will operationally be the test of whether the coefficient of the *OTG/RV* condition term is significantly greater than zero (2-sided test) for each contrast.

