Aim 3: The IV will be group assignment at baseline, the outcome will be treatment participation at the 3-month follow-up time point, the mediators (see Aim 2) will be measured at post-intervention, controlling for baseline. The PROCESS macro for SAS will be used to generate 95% bias corrected confidence intervals for the relative indirect effects as well as all

other parameters. PROCESS can also be used to assess multiple mediators as well as moderated mediation if desired.

Exploratory Analyses: Google Analytics (time spent playing game/viewing website) and EGameFlow data (experience with game functionality and design) will be used to assess any possible moderator effects on the outcome measures. In addition, demographic variables will be explored as moderators.

Qualitative Data Analysis

The further examination of Aims 2 and 3 via semi-structured interviews with clients and clinicians will include thematic analyses of the interviews to provide context and aid in interpretation of quantitative data. Interviews will be recorded and transcribed. We will begin with an a priori coding system for theme identification, developing a codebook with specific codes based on protocol questions but allowing for open coding as themes emerge during analysis. Data will be coded individually by multiple team members. After initial data analysis using NVivo qualitative data analysis software, the research team will discuss and review the emerging codes, establish intercoder agreement, refine constructs and coding categories, identify core themes and generate hypotheses about patterns in the data, and explore additional aspects of the data.

PROTECTION OF SUBJECTS AND USE OF INFORMED CONSENT

The research described in the Phase II proposal of *OnTrack>An Online Role-Playing Game (OnTrack>The Game or OTG)* involves data collected from clients who have been referred to OnTrackNY sites. It also includes qualitative interviews with clinicians. The Center for Social Innovation (C4) and the Research Foundation for Mental Hygiene, Inc. (RFMH) at the New York State Psychiatric Institute (NYSPI) and Columbia University will respect the confidentiality of individuals participating in the study and will obtain Institutional Review Board (IRB) approval through NEIRB and any other local IRBs for all research activities.

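### The primary aim covers seven unranked measures with no primary outcome, alpha, multiplicity procedure or success rule, and the stated test direction does not fit the stigma scales

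*Combined protocol and SAP*

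**What the plan says.** The primary research aim is to evaluate the game "in increasing empowerment, decreasing stigma concerns, and improving treatment engagement". None of the three domains is put first.

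- **Hypothesis 1:** OTG participants, compared with RV, "will report significantly increased empowerment at 2 months post-intervention compared to baseline". It names no scale. The empowerment domain has three.
- **Hypothesis 2:** at 5 months it lists three empowerment scales, two stigma scales expected to fall, "and greater treatment engagement" measured by the SOLES and by engagement with the program. The measures table gives the last item as "Number of unduplicated visits during the follow-up period is above engagement threshold", at follow-up only.
- **Data Analysis, Aim 2:** "A Generalized Linear Mixed Model will be used with the outcome measures listed above as the dependent variables and treatment group" (OTG or RV) as the term of interest. Hypotheses 1 and 2 are judged by whether the OTG/RV "condition term is significantly greater than zero (2-sided test) for each contrast". The same paragraph says: "Post hoc analyses will include assessment of treatment group differences in the outcome measures at post-intervention and 3-month follow-up". It also refers to engagement, in the singular, as binary.
- **Data Analysis, Aim 3:** PROCESS "will be used to generate 95% bias corrected confidence intervals for the relative indirect effects". This is the only confidence or significance level in the document, and it does not concern Aim 2.

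**The concern.** The plan lists what will be tested but not what would count as support for the primary aim. Several measures are each tested, and nothing says whether one, some or all must be significant. A single favourable scale could be presented as support at an error rate above that of one test. A mixed result, such as one of three empowerment scales significant, has no agreed reading.

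Two features of the wording add to this. Time-specific group differences are called post hoc, although both hypotheses are tied to a time point, so it is unclear which tests are confirmatory. And a coefficient above zero means more stigma if a higher score means more stigma, whereas Hypothesis 2 predicts less. The plan does not say that any scale is reverse-scored.

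**Working it through.** **Inputs from the documents.** Measures: 3 + 2 + 2 = 7 (Hypothesis 2 and the measures table). Hypothesis 1: three scales at 2 months. Two-sided test (Aim 2). 200 clients, 1:1 (Research Design). Attrition 10% at 2 months and 20% at 5 months (Recruitment), so 200 × 0.9 / 2 = 90 and 200 × 0.8 / 2 = 80 per arm.

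**Assumed, because the documents do not give them.** Level 0.05 per test, hence 0.025 in the favourable direction; any one favourable significant result counts as support; correlations among the test statistics. The plan has no error-rate or power figure to reproduce.

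**1. How many tests?** With k independent tests of an ineffective game, the chance of at least one favourable result is 1 − 0.975^k.

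| Reading | k | Independent |
|---|---|---|
| One coefficient per outcome, engagement a single binary outcome | 6 | 14.1% |
| One coefficient per outcome, seven measures | 7 | 16.2% |
| Hypothesis 1 (3) plus Hypothesis 2 with a single engagement outcome (6) | 9 | 20.4% |
| Hypothesis 1 (3) plus Hypothesis 2 (7) | 10 | 22.4% |
| Six measures at both later visits plus the visit measure once (6 × 2 + 1) | 13 | 28.0% |

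**2. Correlated tests.** For normal statistics with common correlation r, the chance is 1 − ∫ Φ((1.96 − √r·u)/√(1 − r))^k φ(u) du.

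| r | 3 tests (Hypothesis 1) | 7 tests | 10 tests |
|---|---|---|---|
| 0 | 7.3% | 16.2% | 22.4% |
| 0.3 | 6.8% | 13.7% | 17.8% |
| 0.5 | 6.3% | 11.5% | 14.4% |
| 0.9 | 4.2% | 5.7% | 6.4% |

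A simulation with correlation 0.5 within domains, 0.2 between domains and 0.5 across time gave 13.6% for seven tests and 17.9% for ten. With 0.9, 0.8 and 0.9 it gave 6.8% and 8.1%.

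**3. Conjunctive reading of Hypothesis 2.** If all seven measures must be significant in the beneficial direction, false support needs every ineffective measure to pass, so its probability is at most 2.5%. Hypothesis 1 still has three scales and no rule (first column of the table above).

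**4. Holm over ten tests.** The two-sided familywise error is at most 5%. Simulated false support in the favourable direction was 2.5% with independent tests, 2.0% with correlation 0.5 between scales and 0.6 across time, and 0.9% with 0.9 and 0.9. This is not a general bound: a rejection in the wrong direction relaxes the later thresholds, and two null tests correlated at −0.5 or −0.9 give 2.7% or 3.0%.

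**5. Power cost.** Detectable effect d = (z(1 − α/2) + 0.8416) × √(2/n), for continuous measures.

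- Holm's first step over ten, n = 80: (1.960 + 0.842) × 0.158 = 0.44 SD at α = 0.05; (2.807 + 0.842) × 0.158 = 0.58 SD at α = 0.005. An effect with 80% power at 0.05 then has Φ(2.802 − 2.807) = 50%. If all ten effects are real and of that size, simulated average power per measure under Holm is about 60%.
- Holm's first step over three, n = 90: 0.42 SD rises to 0.48 SD; 80% power falls to Φ(2.802 − 2.394) = 66%.
- All seven must succeed, each with 80% power: 0.8^7 = 21% if independent, 45% at r = 0.5, 67% at r = 0.9.

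These figures ignore team clustering and the planned baseline adjustment. At an assumed baseline correlation of 0.6, the adjustment multiplies the detectable effects by √(1 − 0.36) = 0.8, so 0.44 and 0.58 become 0.35 and 0.46.

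**The case against.** The strongest reply is that the inflation is not a property of the plan. No sentence says that one significant measure is enough. Hypothesis 2 joins its domains with a conjunction, which can be read as requiring all of them. Another ordinary reading is that each measure is reported on its own, at its own nominal error. The reference to each contrast follows a sentence about two time points, so it may mean contrasts over time rather than over measures. All of this stands, and it makes the percentages conditional. It does not supply the missing rule: the plan does not choose among these readings, and none of them settles Hypothesis 1.

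It may also be said that the measures are correlated, which reduces inflation. That is so, but about 6% is reached only if r is near 0.9 throughout, including between a chart-based visit indicator and scales of hope and stigma. Moderate values are a more natural working range.

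Finally, the document refers to a fuller proposal for other matters, and an outcome ranking or alpha could be there. The point therefore covers the supplied text only.

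**Conclusion.** The point holds as an unspecified decision rule. The primary aim has seven unranked measures and no primary outcome, Aim 2 alpha, multiplicity procedure or success rule. The number of confirmatory tests is not settled, and the written direction is wrong for the stigma scales. On an assumed two-sided 0.05 level and an any-one-counts rule, false support is about 11–14% for seven tests and 14–18% for ten at correlations of 0.3 to 0.5, against 2.5% for one test.

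A reader might infer that the trial has a false-positive rate of 16–22%. The documents do not support that: those figures also need independent tests, and neither the level nor the rule behind them is in the plan. Nor should a reader infer that the sponsor means to count a rise in stigma as success. Hypothesis 2 predicts a fall, so the fault lies in the wording of the test criterion. The matter should be settled before outcomes are compared by arm.

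**What to change.** In the Aim 2 paragraph of Data Analysis:

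1. Replace the positive-coefficient criterion with the beneficial direction of each measure.
2. State a two-sided familywise alpha of 0.05 and say which tests are confirmatory, so that the label post hoc no longer covers the comparisons on which Hypotheses 1 and 2 depend.
3. Choose one of the following before unblinding:
   - **One primary.** Name one measure at one time point and make the rest secondary. There is no alpha penalty, and the cost is wording only.
   - **All measures.** State the family (ten tests, or whichever count is meant) and apply Holm across it. Claim support only for measures significant after adjustment in the beneficial direction, and report unadjusted estimates with confidence intervals. The cost is power: for an effect with 80% power at 0.05, about 50% at the first step, and about 60% on average per measure when all ten effects are real.
   - **Conjunctive Hypothesis 2.** If this is meant, say that all its measures must be significant in the beneficial direction, and apply Holm to Hypothesis 1's three scales. The 0.05 then holds for each hypothesis separately. To keep one family, enter Hypothesis 2's largest p-value as a fourth in that Holm. The cost is the low chance that all seven measures succeed together (21% to 67% in the cases above).

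No new data are needed under any choice.

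### Aim 3 names no baseline engagement covariate, so prior engagement may confound the mediator-to-engagement path; baseline SOLES is already collected and should be added

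*Combined protocol and SAP*

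**What the plan says.** Hypothesis 3 proposes that changes in hope, treatment attitudes, self-efficacy and stigma concerns by the end of treatment "will partially mediate the improvement in treatment engagement at follow-up".

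Under Quantitative Analysis, Aim 3 makes group assignment the independent variable and states that "the outcome will be treatment participation at the 3-month follow-up time point". This is the visit 5 months after baseline (2 months of intervention plus 3). It then says that "the mediators (see Aim 2) will be measured at post-intervention, controlling for baseline". The PROCESS macro will produce "95% bias corrected confidence intervals for the relative indirect effects". No other covariate is named.

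Aim 2 does name its adjustment: "Baseline outcome measures and any covariates determined from preliminary analyses will also be included in the model". That sentence describes the Aim 2 mixed model, and nothing carries it over to the PROCESS models.

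The table of quantitative measures (Data Collection) lists two measures of treatment engagement under Aims 2 and 3. SOLES is taken at baseline, post-intervention and follow-up. The other, "Number of unduplicated visits during the follow-up period is above engagement threshold", is marked at follow-up only. The text above the table adds that "Data on treatment engagement will be extracted from clinic charts".

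**The concern.** Randomisation protects the path from arm to mediator. It does not protect the path from mediator to engagement. A client who was already more engaged at entry may report more hope or less stigma at 2 months and may also attend more later. Adjusting for the baseline mediator blocks this route only in part: what remains is any link between prior engagement and the 2-month mediator that the mediator's own baseline does not carry.

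Three features of the design make such a link plausible, though none proves it:

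- In both arms, clinicians are asked to raise the game or website with clients (Study Conditions), so clients who attend more can receive more of that contact after baseline.
- Hypothesis 3 counts attitudes toward treatment among the mediators, a construct close to engagement itself.
- Clients may enter at any point in their first year in the programme (Client Inclusion Criteria), so engagement histories can differ.

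At stake is the mechanism claim. If the game does raise hope or lower stigma, the trial could report that this is how it improves engagement when the association comes from prior engagement. This is a client-level problem, separate from clustering by team and from the type of confidence interval.

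**Working it through.** **No figure to reproduce.** The documents give no effect size, path coefficient, engagement rate or power calculation for Aim 3. The check is therefore by formula and simulation, with assumptions stated.

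**Inputs from the documents.** 200 clients, 1:1. Attrition is 10% at 2 months and 20% at 5 months, leaving 200 × 0.9 = 180 with mediators and 200 × 0.8 = 160 at follow-up. Engagement is treated as binary, as Aim 2 states.

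**Assumed inputs.**
- Game effect on the mediator, *a*: 0 or 0.5 SD.
- Coefficient of the baseline mediator on the 2-month mediator: 0.6.
- Correlation of prior engagement with the baseline mediator: 0.3.
- Effect of prior engagement on the 2-month mediator beyond its baseline, *g*: 0 to 0.3 SD per SD.
- Effect of prior engagement on later engagement, *c*: 0.5 or 1.0 log-odds per SD.
- Reliability of baseline SOLES: 1.0 or 0.6.
- True effect of the mediator on engagement: zero.

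**Expected bias.** If prior engagement is omitted, the spurious indirect effect is approximately

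*a* × *c* × δ, with δ = 0.91*g* / (0.91*g*² + *v*).

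Here 0.91 = 1 − 0.3² is the variance of prior engagement given the baseline mediator, and *v* = 0.64 − *g*² − 0.36*g* is the mediator's residual variance (total within-arm variance 1). Worked for *g* = 0.3:

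- *v* = 0.64 − 0.09 − 0.108 = 0.442
- δ = 0.273 / (0.0819 + 0.442) = 0.521
- with *a* = 0.5 and *c* = 1.0, bias = 0.5 × 1.0 × 0.521 = 0.261 log-odds

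Likewise δ = 0.322 at *g* = 0.2 and 0.151 at *g* = 0.1. The product form shows that all three links are needed: if *a*, *c* or *g* is zero, the bias is zero.

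**Simulation.** n = 160, 1500 trials per row, *a* = 0.5. The mediator model is linear and the engagement model logistic. A Monte Carlo 95% interval for the product stands in for the bias-corrected bootstrap. False mediation means that this interval excludes zero.

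| *g* | *c* | Bias, formula | Bias, simulated | False mediation, baseline mediator only | Plus baseline engagement, error-free | Plus SOLES, reliability 0.6 |
|---|---|---|---|---|---|---|
| 0 | 0.5 | 0 | 0.001 | 4.8% | 5.4% | not run |
| 0 | 1.0 | 0 | 0.001 | 4.9% | 5.2% | not run |
| 0.1 | 0.5 | 0.038 | 0.036 | 5.9% | 5.4% | not run |
| 0.1 | 1.0 | 0.075 | 0.063 | 8.2% | 5.2% | not run |
| 0.2 | 0.5 | 0.081 | 0.081–0.083 | 10.1–11.7% | 5.5% | 6.4% |
| 0.2 | 1.0 | 0.161 | 0.141–0.143 | 21.5–23.5% | 5.0% | 8.6% |
| 0.3 | 0.5 | 0.130 | 0.127–0.128 | 18.5–18.8% | 4.6% | 7.7% |
| 0.3 | 1.0 | 0.261 | 0.229–0.236 | 46.1–49.4% | 5.1% | 13.6% |

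Where a range appears, the same setting was run twice and the difference is simulation error. The formula is a linear approximation and runs slightly high at *c* = 1.0, because omitting a strong predictor shrinks logistic coefficients. With *a* = 0, false mediation stays at or below 1.9% with or without the extra covariate.

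**Sensitivity to the assumptions.** A second set used n = 180, 60% above the visit threshold, baseline mediator coefficient 0.6, correlation 0.4 between prior engagement and the baseline mediator, and a joint-significance test. Rates are for the model with the baseline mediator only:

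| Game effect on mediator | Correlation of prior engagement with later participation | *g* = 0.1 | *g* = 0.2 | *g* = 0.3 |
|---|---|---|---|---|
| 0.4 SD | 0.5 | 7% | 21% | 49% |
| 0.4 SD | 0.3 | 6% | 11% | 18% |
| 0.4 SD | 0.2 | 5% | 7% | 11% |
| 0.2 SD | 0.3 | 3% | 5% | 10% |

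The direction is stable. The size depends on inputs that the documents do not give.

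**The case against.** The strongest reply is that the wording is loose rather than wrong. The phrase about baseline closes a sentence that lists the independent variable, the outcome and the mediators, and it could be meant to cover all of them. A reader might infer that the plan adjusts the mediators alone and that the phrase cannot reach the outcome. The documents do not support that. They do not define treatment participation, and SOLES, which has a baseline value, is listed as an engagement measure for Aims 2 and 3. If SOLES is the Aim 3 outcome, its baseline may be intended. This stands, and it limits the point to the natural reading. It does not remove the need for a change: if participation means the visit threshold, that measure has no scheduled baseline value, and under either reading prior engagement is not named.

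A reader might also infer that Hypothesis 3 will be decided by whether the interval excludes zero. The plan says only that intervals will be produced, so that criterion is the yardstick of this check and not a rule in the plan.

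It is also fair to say that the size is assumed throughout, that every mediation analysis carries some unmeasured confounding of this kind, and that one covariate does not cure it. All of that stands. It argues for modest claims, not for leaving out a relevant covariate that is already collected.

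**Conclusion.** The point holds in limited form. Aim 3, on its natural reading, adjusts for the baseline mediators and names no baseline engagement covariate, so prior engagement may confound the mediator-to-engagement path. Under the assumptions shown, false mediation runs from about 5%, meaning no inflation, to roughly 10% to 50% when confounding is moderate to strong. It is not inflated if the game does not move the mediator.

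These rates should not be read as a forecast for this trial, nor as evidence that a mediation finding would be false. Nor does adding SOLES guarantee nominal error: the return to about 5% requires error-free measurement, and at an assumed reliability of 0.6 the rate is 6% to 14% for *g* of 0.2 to 0.3. The point concerns a secondary aim. The Aim 2 comparisons rest on randomisation and are not affected.

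**What to change.** State the covariates in Aim 3, for example: *Both the mediator regressions and the outcome regression adjust for the baseline value of each mediator and for baseline SOLES.* In the same place, say which engagement measure treatment participation refers to.

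Report the mediation result with the caveat that the mediators were not randomised and that SOLES is an imperfect proxy for prior visits. If pre-enrolment visits can be retrieved from the charts, they could be added as a closer measure. A run with 5-month SOLES as the outcome, adjusted for baseline SOLES, is optional and should be labelled a sensitivity analysis so that it does not become a second test of Hypothesis 3.

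The cost of the main change is one sentence and one covariate, with no new data collection. The estimated indirect effect may be smaller, and some residual confounding will probably remain.

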Following informed consent, the RA will open the envelope indicating to which intervention the participating client was randomized. For people in the *OTG* condition, the RA will review an outline of the game, provide directions on how the game works, and reiterate the expectation that the participant will finish the game in the following 2 months, if not sooner. We expect that spending 1 hour a week playing the game will be sufficient to complete all levels of the game. For participating clients in the *RV* condition, they will be reminded that they are expected to view the recovery videos and download the information materials from the website. We anticipate that the materials could be viewed in approximately 4 hours. The RA will remind the participant that they will receive an email with a link to either the game or the website, depending on their study condition. All participants will be provided with an email address and telephone number. If a participating client does not open the email with the link for 2 weeks, another email will be sent.

Intervention Description (OTG)

The intervention condition will consist of 2 components: (1) provision of the game to the participating clients via an email link, and (2) brief interactions with their mental health provider with respect to reactions they may have when playing the game. Components of the game are described in the *Innovation* section of the proposal. The participant will be reminded via email once a week to play the game/visit the website for a period of 2 months. After that time,

reminders to play the game/visit website will no longer be sent, but the participant may continue to play if they wish.

Control Condition (RV)

The control condition will consist of access to a website that will contain the recovery videos and the static information that is contained in the game. In the control condition, mental health providers will also ask about possible reactions to viewing the recovery videos and information on the website. At the end of the study (after the follow-up assessment), the *RV* participants will be provided access to the game. The table below shows how the conditions align.

Component	OnTrack>The Game (OTG)	Recovery Videos Website (RV)
1. Testimonials of Hope and Recovery	Movie theater zone with 20 brief (3–5 minute) video interviews with young adults who have experienced psychosis.	Online library of the 20 video interviews from OTG

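### Time of use and EGameFlow arise after randomisation, so they cannot serve as moderators of OTG versus RV; the demographic moderators are sound

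*Combined protocol and SAP*

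**What the plan says.** Under Data Analysis, Exploratory Analyses, the plan states that Google Analytics time and EGameFlow data "will be used to assess any possible moderator effects on the outcome measures". It then adds: "In addition, demographic variables will be explored as moderators". No model is given for either analysis.

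The table of quantitative measures under Data Collection places these variables in a block headed "Description of Sample and Potential Moderators and Mediators". Within that block:

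- demographics are marked at baseline only;
- EGameFlow, in the row labelled "Experience with Game Functionality and Design", is marked at post-intervention and follow-up only;
- use, measured by "Springroll Learning Module/Google Analytics", is marked at post-intervention and follow-up only.

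Research Design puts randomisation after the baseline interview. Study Conditions says the emailed link leads to the game or the website according to the assigned condition. It expects about one hour a week of play over two months in OTG. For RV it says: "We anticipate that the materials could be viewed in approximately 4 hours". Under Control Condition (RV), it is only after the follow-up assessment that RV "participants will be provided access to the game".

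**The concern.** A moderator of a randomised comparison has to be something that assignment could not have changed. Time of use and EGameFlow fail that test: neither exists until the client has been allocated and has received a product, and the product differs by arm. Clients with high use in OTG and clients with high use in RV are then different selections of people, and comparing their outcomes is no longer a randomised comparison.

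Each variable also has a problem of meaning. An hour of play is not the same exposure as an hour of viewing. EGameFlow rates a game that RV clients do not have during the study, and the table does not say which arm completes it. If only OTG clients do, an arm-by-EGameFlow effect cannot be estimated. If RV clients rate the website, the two sets of scores describe different products.

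What is at stake is a claim that the game works better for those who play more, made from data in which the game may have no effect.

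**Working it through.** **Timing.** The order in the documents is baseline interview, randomisation, emailed link, use of the product, then the 2-month and 5-month assessments. Use and EGameFlow come after the link; demographics come before randomisation. The validity point follows from this order alone and needs no arithmetic.

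**Size.** The plan gives no error rate or power figure for these analyses, so there is nothing to reproduce. The question is how often an arm-by-use interaction would be significant if neither arm nor use affected the outcome.

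*From the documents:* 200 clients randomised 1:1 and 20% attrition at 5 months, so 200 × 0.8 = 160, or 80 per arm. Expected use is about 8 hours in OTG (1 hour a week for about 8 weeks) and about 4 hours in RV.

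*Assumed:* an unmeasured trait, called motivation here, has correlation ρ with the outcome and r with use, where r may differ by arm. Tests are two-sided at 5%. Four sets of correlations (motivation–outcome, motivation–baseline, baseline–outcome) were used: A (0.5, 0.5, 0.6), B (0.5, 0.3, 0.5), C (0.3, 0.3, 0.6), D (0.3, 0.3, 0.5).

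*By hand, without baseline adjustment.* With no game effect, the slope of a unit-variance outcome on use in an arm is rρ/SD(use). The false interaction is therefore ρ(r_OTG/SD_OTG − r_RV/SD_RV). With use on a unit-SD scale, ρ = 0.5 and r = 0.8 and 0.2:

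- false interaction = 0.5 × (0.8 − 0.2) = 0.30
- mean residual variance = [(1 − 0.40²) + (1 − 0.10²)]/2 = (0.84 + 0.99)/2 = 0.915
- SE = √(0.915 × 2/80) = 0.151
- z = 0.30/0.151 = 1.98, so about 51% of trials would reject.

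The simulation gives 48.4% (set A) and 49.7% (set B). For r = 0.6 and 0.2 the same steps give 0.20/0.154 = 1.30 and about 25%; the simulation gives 24.6% and 23.9%.

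*By simulation.* 6,000 null trials per cell, least squares on arm, use and arm × use, without and with the baseline score. Ranges run over sets A to D.

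| r with motivation, OTG / RV | Unadjusted | Baseline-adjusted |
|---|---|---|
| 0.8 / 0.2 | 20–50% | 9–35% |
| 0.6 / 0.2 | 12–25% | 7–19% |
| 0.6 / 0.5 | 5–6% | 5–6% |
| 0.6 / 0.6 or 0.5 / 0.5 | about 5% | about 5% |
| 0.5 / 0.5 or 0.6 / 0.6, raw hours (SD 4 OTG, SD 2 RV) | – | 6–17% |

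The adjusted column is the more relevant one, because the Aim 2 model says: "Baseline outcome measures and any covariates determined from preliminary analyses will also be included in the model".

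The direction also depends on the assumptions. A stronger use–motivation link in OTG gives a false positive interaction. In raw hours with equal correlations the sign reverses: at ρ = r = 0.5 the slopes are 0.25/4 = 0.0625 per hour in OTG and 0.25/2 = 0.125 in RV.

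**A second simulation** used a different data-generating model (5,000 trials per scenario, 80 per arm, baseline-adjusted). It gave 5.2% when use was unrelated to motivation; 10.8%, 21.5% and 35.7% when the OTG correlation was 0.3, 0.5 and 0.71 with RV at zero; and 69.9% when both were 0.71 but hours were three times as spread in OTG (SD 2.1 against 0.7). With identical links in both arms the interaction test held at 4.8%. In that same scenario, however, the arm effect at mean use was falsely significant in 99.4% of trials, because mean use differed by design (8 against 4 hours). A binary baseline moderator in the same simulated trials was rejected at 4.7–5.5% throughout.

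**The case against.** The plan writes no arm-by-use term, so the criticised model is inferred. An analysis of EGameFlow within OTG alone would fit the text, and the table heading also covers sample description and mediators. The large error rates need a contrast such as 0.8 against 0.2 that nothing in the documents supports. With equal correlations on a common scale there is no inflation, and the raw-hours problem disappears if use is standardised within arm (a rerun of those cells gave 4.1–5.5%). The simulations ignore team clustering and repeated measures. The replacement is itself confounded: within-arm use–outcome associations are often falsely significant. The analysis is already labelled exploratory, and no hypothesis rests on it.

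Most of this limits the size of the problem and leaves the problem itself in place. The paragraph gives these two variables a moderator role and then adds demographics in the same role, which points to arm-by-variable effects. If a within-arm analysis was meant, moderator is the wrong word and the same edit applies. Standardising cures only the case of equal correlations, and the trial cannot show whether that case holds because motivation is not measured. The confounding of within-arm associations is real, and it is why they must be labelled descriptive.

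**Conclusion.** The concern holds as a minor point. That time of use and EGameFlow are not valid moderators of OTG versus RV follows from the plan's own schedule and is firm. The size of the resulting error is not firm. With baseline adjustment the false interaction rate in the main simulation ran from about 5% to 35%, and every correlation and spread behind those figures is an assumption that the documents do not settle. For EGameFlow, an arm interaction is very probably not estimable. The consequence is limited to how exploratory results are read. The primary intent-to-treat tests do not use these variables, and the demographic moderators, measured before randomisation, are unaffected.

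**What to change.** Rewrite the Exploratory Analyses paragraph as follows:

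- limit moderator analyses to variables measured before randomisation (demographics and baseline scores);
- state which arm completes EGameFlow;
- report EGameFlow within OTG, and time of use within each arm separately, as descriptive process or adherence associations with the outcome, adjusted for the baseline score and given with 95% confidence intervals;
- state that these associations are not evidence of moderation or of a dose effect.

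The cost is one paragraph of text and no new data. The plan gives up an exploratory comparison of use between arms. The within-arm associations stay confounded by motivation: with no game effect and 80 OTG clients, the baseline-adjusted use–outcome association was significant in about 9–60% of simulated trials at use–motivation correlations of 0.5–0.6. The descriptive label should therefore carry through to the report.
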